4.2.1 Participant input into design

Not applicable.

4.3 JUSTIFICATION FOR DOSE

The dose selected in this study is the dose approved for the treatment of moderate-to-severe AD patients ≥ 18 years of age for dupixent in the US and EU.

4.4 END OF STUDY DEFINITION

A participant is considered to have completed the study if he/she has completed all phases of the study including end of study (EoS) visit as shown in the schedule of activity (SoA) ([Section 1.3](#) and [Section 1.4](#)).

The end of the study is defined as the date of the last visit of the last participant in the study shown in the SoA ([Section 1.3](#) and [Section 1.4](#)) for the last participant in the trial globally.

5 STUDY POPULATION

A total of 34 AD participants with moderate-to-severe AD and up to 10 healthy participants are to be enrolled in this study. Drop-outs will not be replaced.

Inclusion of healthy participants should be matched for age, gender, race, and anatomical site of skin biopsy. Accordingly, inclusion of healthy participants will start after enrolment of AD participants has been completed. The algorithm for matched healthy participants inclusion will be provided in a separate document.

Prospective approval of protocol deviations to recruitment and enrolment criteria, also known as protocol waivers or exemptions, is not permitted.

5.1 INCLUSION CRITERIA

Participants are eligible to be included in the study only if all of the following criteria apply.

5.1.1 Atopic dermatitis patients

Age

I 01. Male or female of ≥ 18 years of age inclusive, at the time of signing the informed consent form (ICF).

Type of participant and disease characteristics

I 02. Diagnosed with moderate-to-severe chronic AD for at least 1 year before screening.

I 03. Eligible to be treated with dupilumab according to product monograph.

I 04. Pruritus lasting 6 or more weeks before baseline (Day 1).

I 05. Eczema Area and Severity Index (EASI) score ≥ 12 at baseline.

I 06. Pruritus numerical rating scale (NRS) ≥ 4 at baseline.

I 07. Investigator global assessment (IGA) score of ≥ 3 at screening (on the 0 to 4 scale) at baseline.

I 08. Atopic dermatitis active lesions on the upper limbs or lower limbs suitable for a skin biopsy without oozing, bleeding, or infection on upper limbs or trunk.

I 09. Patients with acute AD lesions as determined by Investigator's judgment.

I 10. Participants able to accept skin biopsy procedure.

- I 11. Participants willing to refrain from applying any emollients or topical medications on the target assessment areas (including lesional and non-lesional) throughout the study unless necessary to treat intolerable symptoms.
- I 12. Participants willing and able to comply with all site visit and study-related procedures.
- I 13. Participants able to understand and complete all patient related outcome assessments and questionnaires.

Concomitant medication

- I 14. Stable treatment with non-prohibited medication ([Section 6.5.2](#)) or therapy during the study.

Informed consent

- I 15. Capable of giving signed informed consent which includes compliance with the requirements and restrictions listed in the ICF and in this protocol. In countries where legal age of majority is above 18 years, a specific ICF must also be signed by the participant's legally authorized representative.

5.1.2 Healthy participants

- I 01. Male or female of ≥ 18 years of age inclusive, at the time of signing the ICF.
- I 02. Certified as generally healthy by a comprehensive clinical assessment (detailed medical history and complete physical examination). Well-controlled underlying medical conditions are allowed as long as they do not interfere with assessments or objectives of this study (eg, neurological diseases, neuropathy, skin diseases, chronic pruritus, etc).
- I 03. Participants able to accept skin biopsy procedure.

5.2 EXCLUSION CRITERIA

Participants are excluded from the study if any of the following criteria apply:

5.2.1 Atopic dermatitis patients

Medical conditions

- E 01. Previous treatment with dupilumab stopped within 6 months of baseline due to inadequate response to dupilumab.
- E 02. Skin conditions other than AD that can confound assessments in the opinion of the investigator (ie, skin atrophy, severe photo damage).

- E 03. Regular use (>2 visits per week) of a tanning booth/parlor within 4 weeks of the Screening Visit.
- E 04. Severe concomitant illness(es) that, in the Investigator's judgment, would adversely affect the patient's participation in the study. Examples include, but are not limited to participants with short life expectancy, participants with uncontrolled diabetes (hemoglobin A1c $\geq 9\%$), participants with cardiovascular conditions (eg, Class III or IV cardiac failure according to the New York Heart Association classification), severe renal conditions (eg, participants on dialysis, nephropathy), hepato-biliary conditions (eg, Child-Pugh class B or C), neurological conditions (eg, demyelinating diseases), autoimmune diseases (eg, lupus, inflammatory bowel disease, rheumatoid arthritis, etc), other severe endocrinological, gastrointestinal, metabolic, pulmonary, psychiatric, or lymphatic diseases.
- E 05. Patients with active tuberculosis (TB) or non-TB mycobacterial infection, or a history of incompletely treated TB will be excluded from the study unless it is well documented by a specialist that the participant has been adequately treated and can now start treatment with a biologic agent, in the medical judgment of the Investigator and/or infectious disease specialist. Tuberculosis testing will be performed on a country by country basis, according to local guidelines if required by regulatory authorities or ethics boards.
- E 06. Diagnosed with, suspected of, or at high risk of endoparasitic infection, and/or use of antiparasitic drug within 2 weeks before the Screening Visit (Visit 1) or during the Screening Period.
- E 07. Active chronic or acute infection requiring treatment with systemic antibiotics, antivirals, or antifungals within 2 weeks before the Screening Visit (Visit 1) or during the Screening Period.
- E 08. Known or suspected immunodeficiency, including history of invasive opportunistic infections (eg, TB, histoplasmosis, listeriosis, coccidioidomycosis, pneumocystosis, and aspergillosis) despite infection resolution, or otherwise recurrent infections of abnormal frequency or prolonged duration suggesting an immune compromised status, as judged by the Investigator.
- E 09. Active malignancy or history of malignancy within 5 years before the Baseline Visit, except completely treated in situ carcinoma of the cervix and completely treated and resolved non-metastatic squamous or basal cell carcinoma of the skin.
- E 10. Ocular disorder that in the opinion of the Investigator could adversely affect the individual's risk for study participation. Examples include, but are not limited to, individuals with a history of active cases of herpes keratitis, Sjogren's syndrome, keratoconjunctivitis sicca or dry eye syndrome that require daily use of supplemental lubrication or individuals with ocular conditions that require the use of ocular corticosteroids or cyclosporine.
- E 11. History of systemic hypersensitivity or anaphylaxis to dupilumab or any other biologic therapy, including any excipient.

E 12. Known or suspected alcohol and/or drug abuse.

E 13. Participant with any other medical or psychological condition including relevant laboratory or electrocardiogram abnormalities at screening that, in the opinion of the Investigator, suggest a new and/or insufficiently understood disease, may present an unreasonable risk to the study participant as a result of his/her participation in this clinical trial, may make patient's participation unreliable, or may interfere with study assessments. The specific justification for participants excluded under this criterion will be noted in study documents (chart notes, electronic case report form [eCRF], etc).

Sex

E 14. Pregnant or breastfeeding women, or women planning to become pregnant or breastfeed during the study.

E 15. Women of childbearing potential (see [Section 10.4.1](#)) unwilling to use adequate birth control.

Adequate birth control is defined as agreement to consistently practice an highly effective and accepted method of contraception throughout the duration of the study and for 12 weeks after last dose of study drug (see [Section 10.4.2](#)).

Prior/concomitant medication or therapy

E 16. Intake of any prohibited prior or concomitant medication as specified in [Section 6.5.2](#).

E 17. Planned or anticipated use of any prohibited medications and procedures during screening and study treatment period.

Diagnostic assessments

E 18. Participants with any of the following result at the Screening Visit (Visit 1):

- Positive (or indeterminate) hepatitis B surface antigen (HBsAg) or,
- Positive total hepatitis B core antibody (HBcAb) confirmed by positive hepatitis B virus (HBV) DNA or,
- Positive hepatitis C virus antibody (HCVAb) confirmed by positive hepatitis C virus (HCV) RNA.
- Positive human immunodeficiency virus (HIV) 1/2 serology or history of HIV infection or at the Screening Visit (Visit 1).

Other exclusions

E 19. Individuals accommodated in an institution because of regulatory or legal order; prisoners or participants who are legally institutionalized.

- E 20. Participant not suitable for participation, whatever the reason, as judged by the Investigator, including medical or clinical conditions, or participants potentially at risk of noncompliance to study procedures.
- E 21. Participants are employees of the clinical study site or other individuals directly involved in the conduct of the study, or immediate family members of such individuals (in conjunction with Section 1.61 of the ICH-Good Clinical Practice [GCP] Ordinance E6).
- E 22. Any specific situation during study implementation/course that may rise ethics considerations.
- E 23. Sensitivity to any of the study interventions, or components thereof, or drug or other allergy that, in the opinion of the Investigator, contraindicates participation in the study.
- E 24. Participants suffering from an ailment that makes taking repeat biopsies difficult (blood dyscrasias, anticoagulative use, allergy to local anesthetics etc) or if participant has tattoos at locations of biopsy.

5.2.2 Healthy participants

- E 01. Regular use (>2 visits per week) of a tanning booth/ parlor within 4 weeks of the Screening Visit.
- E 02. Treatment with the following concomitant medications and procedures is prohibited within 4 weeks before the Screening Visit or 5 half-lives (whichever is longer) until EoS Visit:
 - Topical medication.
 - Analgesics.
 - Immunomodulators.
 - Antidepressants.
 - Anti-anxiety drugs.
- E 03. Any Type 2 immune disorders (including, but not limited to atopic dermatitis or asthma), uncontrolled Type 2 diabetes mellitus, Type 1 diabetes mellitus, neuropathy or any other neurological disease.
- E 04. Any concomitant illness(es) or conditions that, in the Investigator's judgment, would adversely affect the subject's participation in the study or potentially affect any skin biopsy related read out.
- E 05. Positive test for immunoglobulin E (IgE) antibodies.
- E 06. Known or suspected alcohol and/or drug abuse.

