6.5.3 Permitted medications

Other than the prohibited medications and procedures listed in [Section 6.5.2](#), treatment with concomitant medications and procedures is permitted during the study. This includes nasal and inhaled corticosteroids. The use of these medications should be recorded.

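### Neuropathy, type 1 diabetes and certain drug classes bar a healthy volunteer outright but an AD participant only by severity, discretion or no specific rule, so the exploratory baseline AD-versus-healthy nerve-fibre comparison is open to confounding

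*Protocol*

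**What the plan says.** **Healthy participants.** Protocol 5.2.2 E03 excludes "uncontrolled Type 2 diabetes mellitus, Type 1 diabetes mellitus, neuropathy or any other neurological disease", with no severity limit on type 1 diabetes, neuropathy or neurological disease. E02 begins "Treatment with the following concomitant medications and procedures is prohibited within 4 weeks before the Screening Visit or 5 half-lives (whichever is longer" and lists analgesics, antidepressants and anti-anxiety drugs, along with topical medication and immunomodulators. E04 adds any illness that could "potentially affect any skin biopsy related read out". Inclusion criterion I02 in 5.1.2 accepts well-controlled conditions only "as long as they do not interfere with assessments or objectives of this study (eg, neurological diseases, neuropathy, skin diseases, chronic pruritus, etc".

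**AD participants.** Protocol 5.2.1 E04 excludes "Severe concomitant illness(es) that, in the Investigator's judgment, would adversely affect the patient's participation in the study". Its examples include uncontrolled diabetes, given as HbA1c of 9% or more, and "neurological conditions (eg, demyelinating diseases". E13 lets the investigator exclude any other condition thought likely to disturb the study assessments, and E20 is a general unsuitability clause. For drugs, 6.5.2 lists what is prohibited and 6.5.3 says that otherwise "treatment with concomitant medications and procedures is permitted during the study".

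**Use of the healthy group.** The synopsis makes it the normal-skin reference, and 6.3 puts it first among the measures to control bias. Comparing neuronal architecture in AD lesional and healthy skin at baseline is an exploratory objective (Section 3). Table 4 in 9.4.7 plans descriptive statistics and plots for it.

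**The concern.** The reference group is cleared of conditions and drugs that may be present in the AD group. If any of them changes nerve fibre density or branching, part of the difference between AD and healthy skin would come from them and not from AD. Protocol 4.2 cites a report that nerve fibres were scarce in the upper epidermis of severely lesioned AD skin. If neuropathy lowers fibre density (an assumption here), it would push the AD group in the same direction and could be read as the disease pattern. At stake is the reading of AD skin against normal skin, and with it any statement about neuronal normalization that uses healthy skin as the yardstick.

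**Working it through.** The documents give no figure to reproduce: 9.2 reports no formal sample size estimation, and no effect size or SD is stated. The check is to run the same person through both sets of criteria.

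| Person | As healthy volunteer | As AD participant |
|---|---|---|
| Mild neuropathy | Excluded (E03) | Not reached by E04 unless judged severe; E13 or E20 only if the investigator invokes them |
| Type 1 diabetes, HbA1c below 9% | Excluded (E03) | Below the E04 diabetes example; E13 or E20 discretionary |
| Stable antidepressant or anti-anxiety drug | Excluded (E02) | Not listed in 6.5.2; permitted by 6.5.3; consistent with I14, which asks for stable treatment |
| Analgesic | Excluded (E02) | Class not listed in 6.5.2; paracetamol up to 2 g/day expressly allowed by 6.5 |
| Antihistamine | Not listed in E02 | Prohibited (6.5.2) |

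The last row shows that the drug asymmetry also runs the other way.

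**Does anything later correct for this?**
- Matching (9.2) uses site, age, gender, race and skin location, as far as possible. It does not use comorbidity or medication.
- Table 4 plans no adjustment or restriction for the AD-versus-healthy comparison.
- The SAP summarises medical history (1.2.3.2) and concomitant medication (1.2.5) but links neither to the biopsy results.
- SAP 1.1 sends biomarker analyses to a separate plan, which is not among the documents.

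**Illustration of size.** All inputs except the group sizes are assumed. Let k AD participants be affected, each shifted by e, in units of a between-participant SD common to both groups.
- Shift in the AD mean = (k/n) × e.
- SE of the AD-minus-healthy difference = √(1/n + 1/10), with 10 healthy participants (the maximum in 9.2).

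For n = 34, SE = √(1/34 + 1/10) = 0.36 SD:
- k = 1, e = 0.5: 1/34 × 0.5 = 0.015 SD, or 0.04 SE.
- k = 5, e = 1.5: 5/34 × 1.5 = 0.22 SD, or 0.61 SE.

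For n = 27 evaluable (34 × 0.8 = 27.2, from the 20% drop-out allowance), SE = √(1/27 + 1/10) = 0.37 SD:
- k = 1, e = 0.5: 1/27 × 0.5 = 0.019 SD, or 0.05 SE.
- k = 5, e = 1.5: 5/27 × 1.5 = 0.28 SD, or 0.75 SE.

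If no such participant enrols, the shift is zero.

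**The case against.** The strongest reply is that a normal reference is meant to be cleaner than a disease group. Healthy E03 and E05 also exclude asthma and a positive IgE test, and nobody would ask AD participants to meet those. Healthy I02 likewise lists skin disease and chronic pruritus, which AD participants must have, so it describes a suitable control and not what invalidates an AD biopsy. This stands to the extent that different criteria are not in themselves an error. It does not explain away neuropathy or neurological disease: these are not part of AD, and the same nerve-fibre assessment is made in both groups.

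Three further replies also have weight:
- The comparison is exploratory and descriptive, without a hypothesis test. This limits the consequence.
- Baseline lesional against non-lesional skin is a within-person contrast free of this problem. However, the non-lesional biopsy is optional (8.3.1).
- The biomarker SAP and the matching algorithm are separate documents that cannot be seen here. Either might already address the point, so nothing can be said about their content.

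A reader might infer three stronger claims, which the documents do not support:
- *That AD participants with these conditions are not excluded at all.* E04 reaches severe neurological conditions and uncontrolled diabetes, and E13 and E20 can reach milder cases. The gap is between a categorical rule and a severity-limited or discretionary one.
- *That the protocol itself says all these factors interfere.* I02 names neuropathy and neurological disease only. Diabetes and the drugs appear only as exclusions, and the one stated worry about an analgesic (6.5) is bias in itch scores.
- *That simply applying healthy E02 to AD participants would cure it.* That would remove users of permitted paracetamol, perhaps users of permitted nasal or inhaled corticosteroids and, read literally after baseline, anyone on dupilumab as an immunomodulator.

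**Conclusion.** The asymmetry is real, and neither the matching factors nor the analysis described in the protocol and SAP accounts for it. The AD-versus-healthy baseline comparison of nerve fibre density and branching is open to confounding. To say that it is confounded would go too far, because that depends on who enrols and on effects that the documents do not give. The range of 0.04 to 0.75 SE rests wholly on assumed numbers and effects, and shows only that the shift could be negligible or could approach the random error of the comparison.

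A reader might also infer that the primary endpoint is compromised. The documents do not support this. It is the Week 17 change within AD participants and does not use healthy skin. Non-prohibited medication is to be kept stable (I14, 5.3), so a constant shift cancels in the absolute change and a proportional one in the percent change. A Week 17 sensitivity analysis on this ground is not needed.

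This is a modest weakness in an exploratory comparison. It deserves a cheap check, because the healthy group is the plan's stated normal reference.

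**What to change.** Eligibility need not change. In the biomarker SAP, or in the existing SAP if the table is produced there, define two flags for AD participants and set them before the biopsy results are examined:
1. **Conditions:** neuropathy, another neurological disease, type 1 diabetes or uncontrolled type 2 diabetes, from the coded medical history.
2. **Drugs:** regular use of antidepressants, anti-anxiety drugs or analgesics at baseline, from the coded medication records. Occasional permitted paracetamol, nasal or inhaled corticosteroids, and dupilumab do not count. Section 6.5 already requires reason, dates, dose and frequency, so regular and occasional use can be told apart.

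Report the number flagged under each heading. Repeat the AD-versus-healthy baseline neuronal architecture table without the flagged participants, as a sensitivity analysis. If nobody is flagged, say so; the question is then closed for these factors.

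The cost is one derived flag variable with two components, one extra table, and somewhat fewer AD participants in that table. One limit should be stated with it: the schedule includes no HbA1c measurement, so the diabetes part rests on what the history records.

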5.3 LIFESTYLE CONSIDERATIONS

- Non-prohibited concomitant medication or therapy should be kept stable during the study; any changes of concomitant medication should be recorded in the eCRF.
- Participants should not apply any emollients on or within 5 cm of the predefined skin assessment areas during the entire study period.

5.3.1 Meals and dietary restrictions

- Participants with a known food allergy should not consume any foods from an outside home provider on the day of the dupilumab injection.
- Alcohol is prohibited for at least 16 hours before each visit and each clinical assessment (if done at home).

5.4 SCREEN FAILURES

Screen failures are defined as participants who consent to participate in the clinical study but are subsequently found to be not eligible to enroll in the study. A minimal set of screen failure information is required to ensure transparent reporting of screen failure participants to meet the Consolidated Standards of Reporting Trials (CONSORT) publishing requirements and to respond to queries from regulatory authorities. Minimal information includes demography, screen failure reasons, eligibility criteria, and any serious AE (SAE).

Note: “Enrolled” means a participant’s, or their legally acceptable representative’s, agreement to participate in a clinical study following completion of the informed consent process. Potential participants who are screened for the purpose of determining eligibility for the study, but do not participate in the study, are not considered enrolled, unless otherwise specified by the protocol.

Rescreening may be allowed once during the open screening period and upon the Investigator’s decision (for certain circumstances, eg, participants cannot start the study due to private reasons). All screening procedures will have to be repeated and a different patient identification number will be assigned. There is no requirement for a waiting period between the screen failure date and the rescreening date. Participants who are rescreened must sign a new consent form and all Visit 1 procedures must be repeated.

6 STUDY INTERVENTION(S) AND CONCOMITANT THERAPY

Study intervention is defined as any investigational intervention(s), marketed product(s), placebo, or medical device(s) intended to be administered to a study participant according to the study protocol.

6.1 STUDY INTERVENTION(S) ADMINISTERED

Study participants will be assigned to study intervention as described below:

- Up to 34 patients with moderate-to-severe AD will receive dupilumab.
 - Dose regimen: Participants will receive a SC loading dose of dupilumab 600 mg on Day 1, followed by Q2W SC dosing of dupilumab 300 mg (2 mL of a 150 mg/mL solution) from Week 3 to Week 15.

One kit number list is generated centrally by Sanofi and IMP is packaged in accordance with this list.

Study intervention will be dispensed at the study visits summarized in SoA (see [Section 1.3](#)). Returned study intervention should not be re-dispensed to the participants.

Table 2 - Overview of study interventions administered

| | |
|--|---|
| ARM name | Dupilumab |
| Intervention name | Dupilumab 300 mg |
| Type | Biological |
| Dose formulation | A 150 mg/mL dupilumab solution in a prefilled syringe to deliver 300 mg in 2 mL |
| Unit dose strength(s) | 300 mg |
| Dosage level(s) | 300 mg every 14 ±2 days after an initial loading dose of 600 mg |
| Route of administration | Subcutaneous ^a |
| Use | Experimental |
| IMP | IMP |
| Packaging and labeling | Each dose of dupilumab will be supplied as 1 glass prefilled syringe packed in a patient kit box. Both glass prefilled syringe and the box will be labeled as required per country requirement. |
| Storage | 2°C to 8°C |
| Current/Former name(s) or alias(es) | Dupixent |

^a Subcutaneous injection sites should alternate between the upper thighs, 4 quadrants of the abdomen, or the upper arms, so that the same site is not injected twice during consecutive administrations. Injection in the upper arms can only be done by the study site staff and/or by a trained person or health care professional but not the participant themselves. Site of injection should be locally distant from the site of skin biopsies.

Investigational medicinal product

The IMP will be administered every 14 ± 2 days (Q2W) during the 16-week treatment period (with the last IMP administration at Week 15).

For the doses that are not scheduled to be given at the study site, administration of IMP at participant's home is allowed after appropriate training of the participant (or parent/legally authorized representative/caregiver). At Visit 2, the Investigator or delegate will prepare and inject the first dose of IMP in front of the participant (or parent/legally authorized participant representative/caregiver). The participant (or parent/legally authorized representative/caregiver) will prepare and inject the second dose of IMP at Visit 3 under the supervision of the Investigator or delegate. The training must be documented in the participant's study file.

In case of emergency (eg, natural disaster, pandemic, etc) different methods of IMP injection training (eg, training remotely with instructions provided by phone, etc) can be performed (and will be documented in the participant's study file). If the participant (or parent/legally authorized representative/caregiver) is unable or unwilling to prepare and inject IMP, injections can be performed at the study site by way of unscheduled visits; or arrangements can be made for qualified site personnel and/or health care professionals (eg, visiting nurse service) to administer IMP at participant's home.

Between the protocol-scheduled on-site visits, interim visits may be required for IMP dispensing. As an alternative to these visits in case of emergency (eg, natural disaster, pandemic, etc), IMP may be supplied from the site to the participant via a Sponsor-approved courier company where allowed by local regulations and approved by the participant.

When the participant has a study visit, the IMP will be administered following clinical procedures and blood collection. Participants should be monitored for at least 30 minutes. The monitoring period may be extended as per country-specific or local site-specific requirements.

Participant/parent/legally authorized representative/caregiver should be trained by the site staff to recognize potential signs and symptoms of hypersensitivity reaction in order to self monitor/monitor at home following injection. In case of hypersensitivity symptoms, the participant should contact their healthcare provider or emergency services.

Subcutaneous injection sites should be alternated among the 4 quadrants of the abdomen (avoiding navel and waist areas), the upper thighs or the upper arms, so that the same site is not injected between two Q2W injections. Injections in the upper arms could be done only by a trained person (parent/legally authorized representative/caregiver trained by Investigator or Delegate) or health care professional but not the participants themselves. Site of injection should be locally distant from the site of skin biopsies.

For doses not given at the study site, eDiary will be provided to record information related to the injections. The eDiary will be kept as source data in the participant's study file.

